9.2.2 Quality of Life Scores

These comprise the Kansas City Cardiomyopathy questionnaire (KCCQ) at 6 months, 1 year and 2 years post randomisation, and the EuroQol EQ-5D-5L at 6 months and then yearly to the end of follow-up.

For both quality of life measures described above, differences in mean levels of the standard outcome measures between treatment groups at each timepoint will be calculated using a linear mixed model with treatment group, categorical treatment by timepoint interaction and baseline standard outcome measure in the model (random intercept, unstructured correlation). It may be necessary to examine the quality of life score for transformations to adhere to the assumptions of the linear mixed model or use bootstrapping techniques if a suitable transformation cannot be found. EuroQol EQ-5D-5L data will also be analysed as part of the health economics outcome (Section 11).

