5.2 Definition of Populations for Analysis

All patients who provide informed consent will be accounted for in this study. A consort flow diagram will be produced to describe the passage of patients through the trial from enrolment, randomisation, treatment, follow-up and analysis. Study withdrawals and major protocol violations will also be indicated.

The primary outcome analysis will be conducted on all randomised patients on an intention-to-treat (ITT) basis, according to treatment groups to which they were randomised, irrespective of whether they undergo their randomised treatment.

The analyses of the secondary outcomes will also be performed on the same ITT population as the primary outcome.

REVIVED is a randomised controlled trial of an initial strategy of PCI compared to OMT, rather than technique, with subsequent revascularisation considered in patients randomised to OMT permitted in certain specific, protocol-defined circumstances. Consequently, a per-protocol analysis of these data is not planned. However, details of patients in the PCI arm not receiving the intended PCI as planned and those patient in the OMT receiving subsequent revascularisation will be presented.

For the description of procedural outcomes, only patients randomised to PCI and who actually received the PCI will be included in the analysis population.

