9.2.1 LVEF on Echocardiography at 6 Months and 1 Year

Baseline, 6-month and 12-month echocardiograms will be anonymised and submitted to an independent echocardiography core laboratory (at Guy's and St Thomas' Hospital, London, UK), which will determine LVEF using a Simpson's biplane method for evaluation of the major secondary outcome. Anonymised scans were read by core laboratory readers who were blinded to treatment assignment and also the timing of each echo in relation to randomisation.

Where echocardiograms were not performed at precise follow-up intervals (for example, due to restrictions related to the COVID-19 pandemic), echocardiograms recorded between 4 months to 9 months post-randomisation will be considered as the planned 6-month measure, those recorded from 9 months to 24 months post-randomisation will be considered as the planned 1-year measure and the mean (SD) delay from randomisation to each echocardiogram reported. For patients who die a

value of 0% will be imputed for the primary analysis with a secondary sensitivity analysis excluding these patients.

The mean % LVEF at 6 months and 1 year in each treatment group, together with the absolute difference between these measures (and its associated p-value and 95% confidence interval), will be estimated using a linear mixed effects model for repeated measures as described by Frost, Kenward and Fox.¹

This linear mixed model is an extension of a simpler model suggested by White and Thompson as an alternative to the standard analysis of covariance (ANCOVA) model commonly used for the analysis of clinical trials with only a single follow-up measure of the outcome plus a baseline measure. Key features of the White and Thompson model are that the baseline measure is included in the model as an additional outcome that is allowed to be correlated with the follow-up measure, and whose mean is assumed to be the same in both arms of the trial. In the absence of missing data, the White and Thompson model gives identical effect estimates and virtually identical standard errors to the more standard ANCOVA model. Where there are missing data, the White and Thompson approach has the advantage that patients for whom the follow-up measure is present but the baseline measure is missing can be included in the analysis. It also extends naturally to the model proposed by Frost, Kenward and Fox for the situation where there are multiple follow-up measures.

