Like the White and Thompson model, this model includes the baseline measure of % LVEF as an additional outcome variable. It includes time in the model as a categorical variable (baseline, 6 months and 1 year), random intercepts, an interaction between time (categorical) and treatment group, and assumes no effect of treatment at baseline (as with the White and Thompson model). The model uses an unstructured variance-covariance matrix, and allows the baseline and follow-up measures of LVEF to be correlated. This type of model has been used previously to analyse clinical trial data.^{3,4} If there were only a single follow-up measure, this model would be equivalent to the White and Thompson model referred to earlier.

It may be necessary to examine % LVEF for transformations to adhere to the assumptions of the linear mixed model or use bootstrapping techniques if a suitable transformation cannot be found.

An analysis of site reported LVEF will also be undertaken as a sensitivity analysis.

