9.3 Analysis of Other Secondary Endpoints

Analysis of secondary outcomes will be based on the ITT population unless otherwise stated below.

- (1) Cardiovascular death over the entire duration of follow-up
- (2) All-cause death over the entire duration of follow-up
- (3) Hospitalisation due to heart failure over the entire duration of follow-up

- (4) Acute MI over the entire duration of follow-up (until last scheduled annual follow-up visit)
- (5) Appropriate ICD therapy to 2 years post randomisation
- (6) Unplanned further revascularisation over the entire duration of follow-up (until last scheduled annual follow-up visit)
- (7) CCS class at 6 months, 1 year and 2 years post randomisation
- (8) NHS Resource use
- (9) Brain natriuretic peptide (BNP or NT-Pro BNP) level at 6 months, 1 year and 2 years post randomisation
- (10) Major bleeding to 2 years post randomisation (recorded post PCI, 6 months,1 year and 2 years)

The above secondary time to event outcomes (1-6) will be analysed using the same methods as described for the primary outcome (Section 9.1). CSS class, which is an ordinal outcome measure scored 0-4, will be analysed using the same methods as described for 'NYHA Functional Class' outcome (Section 9.2.3). Analysis of NHS resource use is described in the health economics outcome section (Section 11). Differences in mean BNP or NT-Pro BNP between treatment groups at each timepoint will be calculated using a linear mixed model with treatment group, categorical treatment by timepoint interaction and baseline BNP or NT-Pro BNP in the model (random intercept, unstructured correlation) as described for % LVEF (Section 9.2.1). It may be necessary to examine BNP or NT-Pro BNP for transformations to adhere to the assumptions of the linear mixed model or use bootstrapping techniques if a suitable transformation cannot be found.

Major bleeding will be summarised as the cumulative frequency and percentage at each time point by treatment group. The treatment groups will be compared at 1 and 2 years using a risk ratio, 95% confidence interval and likelihood ratio test p-value from a binomial regression model.

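### Section 9.2.2 of the main trial SAP reads as a baseline-covariate model for KCCQ and EQ-5D-5L, so patients without a baseline score would drop out unless imputed; the SAP's LVEF model keeps them

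*Protocol*

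**What the plan says.** **LVEF (main trial SAP 9.2.1).** The SAP says that "this model includes the baseline measure of % LVEF as an additional outcome variable". Time is categorical and includes baseline, and the treatment effect at baseline is set to zero. Random intercepts and an unstructured variance-covariance matrix are specified. One stated advantage of this family of models is that "patients for whom the follow-up measure is present but the baseline measure is missing can be included in the analysis".

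**KCCQ and EQ-5D-5L (9.2.2).** The section opens: "These comprise the Kansas City Cardiomyopathy questionnaire (KCCQ) at 6 months, 1 year and 2 years post randomisation". EQ-5D-5L follows at 6 months and then yearly. The mixed model lists treatment group, a treatment by timepoint interaction and "baseline standard outcome measure in the model", with a random intercept and unstructured correlation. It does not say that baseline is an outcome, sets no constraint at baseline and does not refer to 9.2.1.

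**BNP/NT-proBNP (9.3).** The term list has the same form, but it ends with a pointer: "baseline BNP or NT-Pro BNP in the model (random intercept, unstructured correlation) as described for % LVEF".

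**Population and missing data.** Section 5.2 states: "The analyses of the secondary outcomes will also be performed on the same ITT population as the primary outcome". Section 6.5.2 says that modelling and imputation will be considered according to the amount and pattern of missing data, and refers to 9.2.1. Section 6.5.5 also refers to 9.2.1 for baseline adjustment of continuous secondary outcomes.

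**The concern.** A mixed model tolerates missing outcomes but not missing covariates. If baseline KCCQ is a covariate and is absent, all of that patient's follow-up scores leave the analysis unless the baseline is imputed. Section 9.2.1 describes this weakness and chooses a model that avoids it. Section 9.2.2 gives two major secondary endpoints a differently worded model with no reason for the difference.

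Missing baselines are possible, because neither questionnaire is among the tests required for eligibility (protocol 16.1). What is at stake is precision, the avoidable loss of patients with usable follow-up, and a modelling choice that 9.2.2 leaves open.

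**Working it through.** **Step 1. Which model does 9.2.2 describe?**

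| Feature | LVEF (9.2.1) | KCCQ, EQ-5D-5L (9.2.2) |
|---|---|---|
| Role of baseline | Additional outcome | Listed as a separate model term |
| Timepoints named | Baseline, 6 months, 1 year | Follow-up visits only |
| Treatment main effect | Not listed | Listed |
| Treatment effect at baseline | Set to zero | Not mentioned |
| Pointer to 9.2.1 | Not applicable | None |

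The word covariate does not appear in 9.2.2, but the listed terms fit that reading best. If baseline were an outcome there, a free treatment main effect would let the arms differ at baseline, which the 9.2.1 model rules out.

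**Step 2. Loss of precision under the covariate reading, without imputation.**

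The documents give no figure to reproduce. The inputs are:
- 700 patients (SAP 4.2)
- proportion m with a missing baseline: assumed 2% to 20%
- baseline to follow-up correlation ρ: assumed 0.4 to 0.7

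Take one follow-up time and outcome variance 1. A patient with a baseline score carries information 1/(1−ρ²) on the treatment effect. A patient without one carries information 1 if baseline is an outcome, and 0 if baseline is a covariate.

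- Covariate model: (1−m)/(1−ρ²)
- Baseline-as-outcome model: (1−m)/(1−ρ²) + m
- Ratio of standard errors, covariate to outcome model: √[1 + m(1−ρ²)/(1−m)]

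Example with m = 0.10 and ρ = 0.4: √(1 + 0.10 × 0.84/0.90) = √1.0933 = 1.0456, a rise of 4.6%.

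| m (assumed) | Patients lost of 700 | Rise in SE, ρ = 0.7 | Rise in SE, ρ = 0.4 |
|---|---|---|---|
| 0% | 0 | 0% | 0% |
| 2% | 14 | 0.5% | 0.9% |
| 5% | 35 | 1.3% | 2.2% |
| 10% | 70 | 2.8% | 4.6% |
| 20% | 140 | 6.2% | 10.0% |

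Counting lost patients alone gives 1/√(1−m) − 1, which is 2.6% at 5% missing and 5.4% at 10%. The formula above reduces to this at ρ = 0, so these figures are an upper bound and not an expected size.

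**Step 3. Bias.**

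Protocol 16.2 places baseline KCCQ, EQ-5D-5L and BNP up to 6 months before randomisation. Whether such a baseline is missing cannot depend on the allocated arm, so the remaining patients are still a randomised comparison.

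A simulation checked this, with 2,000 runs of 700 patients, ρ = 0.6, a true effect of 0.3 SD and about 10% of baselines missing. The bias from dropping those patients was:
- −0.0001 SD when missingness was completely random
- −0.002 SD when missingness depended on baseline severity

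The estimates had an SD of about 0.065 across runs, so the Monte Carlo error of the mean is about 0.065/√2000 = 0.0015. Neither figure is distinguishable from zero in practice.

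**The case against.** **The wording is shorthand for the 9.2.1 model.** Section 9.2.2 says only that baseline is in the model, and 9.2.1 uses a similar phrase when baseline is an outcome. The random intercept and unstructured correlation match 9.2.1. The BNP text in 9.3 uses the same term list and then refers to 9.2.1, and sections 6.5.2 and 6.5.5 also point there. This has weight: the covariate reading is the natural one, not the only one, and dropping patients also presumes no imputation, which 6.5.2 leaves open. But 9.2.2 has no pointer of its own, names only follow-up visits and lists a treatment main effect. A programmer could reasonably fit the covariate model.

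**LVEF may need the model more.** Protocol 10.2 has some baseline echocardiograms done after randomisation, so a model that tolerates missing baselines matters more for LVEF. That could justify different handling, but the SAP does not give it as a reason.

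**Stronger readings that the documents do not support.**
- A reader might infer that BNP/NT-proBNP patients are excluded. The pointer in 9.3 ties that analysis to 9.2.1. At most, the term list and the pointer fit together poorly.
- A reader might infer a breach of intention to treat. Section 5.2 defines it as analysis by randomised group irrespective of treatment received, and a missing measurement does not violate that.
- A reader might infer a biased treatment comparison. Step 3 of the working shows no material bias when baselines are taken before randomisation.

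**Conclusion.** The point holds as a minor one, for KCCQ and EQ-5D-5L. On its natural reading, 9.2.2 fits a model that loses patients with follow-up but no baseline score unless baselines are imputed, while 9.2.1 already gives a model that keeps them.

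The effect is on precision: standard errors about 1.3 to 2.2% larger at 5% missing and 2.8 to 4.6% larger at 10%, with no effect if nothing is missing. These figures rest on assumed missing rates and correlations, a single follow-up time, and follow-up that is equally complete with and without a baseline score.

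The finding of no material bias rests on baselines being collected before randomisation, as the protocol plans. If the treatment effect itself differed in patients without a baseline score, dropping them would shift the average effect being estimated, though the comparison would still be randomised. For BNP/NT-proBNP the point is only one of wording.

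**What to change.** In main trial SAP 9.2.2, state that KCCQ and EQ-5D-5L are analysed with the 9.2.1 model:
- baseline score as an additional outcome
- categorical time that includes baseline and each scheduled follow-up visit for that instrument
- time by treatment interaction, with no treatment effect at baseline and no separate unconstrained treatment term
- the covariance structure stated in 9.2.1

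In 9.3, rewrite the BNP/NT-proBNP term list so that it agrees with the existing pointer to 9.2.1.

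The cost is a few sentences of SAP wording. No extra data are needed, and the method is one that the SAP already describes and justifies. With complete data, 9.2.1 itself notes for the single-follow-up case that this approach and standard covariate adjustment give the same estimates and almost the same standard errors, so little is lost if few baselines turn out to be missing.

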9.2.3 NYHA Functional Class at 6 Months, 1 year and 2 years

NHYA class is an ordinal outcome measure scored as I, II, III or IV. NYHA class will be summarised as frequency and percentage in each category, by treatment group and timepoint. Ordered logistic regression adjusted for baseline NYHA class will be used at each timepoint (conditional on surviving to that point) to compare treatment groups by estimating the proportional odds ratio (95% confidence interval) for a higher NYHA class and associated likelihood ratio test p-value.

As a sensitivity analysis, deaths before a timepoint will be assigned a NYHA class of V and included in the analysis at that timepoint. For each model, the assumption of proportional odds will be assessed graphically by estimating the odds ratio (95% confidence interval) for each cutpoint of the outcome and more formally using the Brant test. If there is clear evidence against the proportional odds assumption, comparisons will also be made by dichotomising the outcome or using appropriate non-parametric methods.^{5,6}

9.3 Analysis of Other Secondary Endpoints

Analysis of secondary outcomes will be based on the ITT population unless otherwise stated below.

- (1) Cardiovascular death over the entire duration of follow-up
- (2) All-cause death over the entire duration of follow-up
- (3) Hospitalisation due to heart failure over the entire duration of follow-up

- (4) Acute MI over the entire duration of follow-up (until last scheduled annual follow-up visit)
- (5) Appropriate ICD therapy to 2 years post randomisation
- (6) Unplanned further revascularisation over the entire duration of follow-up (until last scheduled annual follow-up visit)
- (7) CCS class at 6 months, 1 year and 2 years post randomisation
- (8) NHS Resource use
- (9) Brain natriuretic peptide (BNP or NT-Pro BNP) level at 6 months, 1 year and 2 years post randomisation
- (10) Major bleeding to 2 years post randomisation (recorded post PCI, 6 months,1 year and 2 years)

The above secondary time to event outcomes (1-6) will be analysed using the same methods as described for the primary outcome (Section 9.1). CSS class, which is an ordinal outcome measure scored 0-4, will be analysed using the same methods as described for 'NYHA Functional Class' outcome (Section 9.2.3). Analysis of NHS resource use is described in the health economics outcome section (Section 11). Differences in mean BNP or NT-Pro BNP between treatment groups at each timepoint will be calculated using a linear mixed model with treatment group, categorical treatment by timepoint interaction and baseline BNP or NT-Pro BNP in the model (random intercept, unstructured correlation) as described for % LVEF (Section 9.2.1). It may be necessary to examine BNP or NT-Pro BNP for transformations to adhere to the assumptions of the linear mixed model or use bootstrapping techniques if a suitable transformation cannot be found.

Major bleeding will be summarised as the cumulative frequency and percentage at each time point by treatment group. The treatment groups will be compared at 1 and 2 years using a risk ratio, 95% confidence interval and likelihood ratio test p-value from a binomial regression model.

Appropriate ICD therapy will be assessed, on an ITT basis, in the cohort that had undergone device implantation before randomisation or within 90 days of randomisation. The main analysis will only include centre-reported ICD data up to 2 years from randomisation. Longer term ICD-derived outcomes will be the subject of a separate sub-study. See also section 9.6.2 below.

For death, MI, unplanned revascularisation, heart failure hospitalisation and appropriate ICD therapy outcomes, further details of these outcomes will be REVIVED SAP

summarised by treatment group (e.g. primary causes of death, NSTEMI or STEMI, reason for revascularisation and type of revascularisation, days in hospital, types of therapies). Continuous variables will be described by the means and standard deviation. Alternatively for skewed variables they may be described by the median and IQR. Categorical variables will be described by frequency and percentages in each category.

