8.3. Statistical Analysis

A detailed statistical analysis plan will be finalised before any analysis of the data by treatment group is undertaken. An unadjusted time-to-event analysis will be performed on the primary endpoint using data across all follow-up, with time to the first event (or censoring) times measured from randomisation. Hazard ratios together with associated confidence intervals will be calculated from the Cox proportional hazards model. The assumptions underlying the Cox model will be assessed. If there is clear non-proportionality, comparisons will also be made in early and later follow-up with cut-points determined based on availability of data prior to unblinding. Cumulative event rates will be calculated and presented using Kaplan-Meier time-to-event curves. As a measure of absolute treatment difference, cumulative event rates will be compared at 2 years. Secondary analyses of each individual component of the primary composite endpoint as well as other secondary time to event outcomes will be analysed using the above methods. Losses to follow-up are expected to be minimal and patients will be included up until the time they experience the event or are censored.

Any categorical outcome measures will be examined at specific time points using risk ratios or risk differences, confidence intervals and chi-square or Fisher's exact tests as appropriate. Continuous variables will be analysed and presented as mean treatment differences, confidence intervals and p values derived from analysis of co-variance models or unpaired t-tests as appropriate (with appropriate transformation if necessary). Analysis of endpoints in the randomised cohort will be by intention-to-treat.

A limited number of subgroups for the primary endpoint will be pre-specified in the analysis plan and are likely to include groups stratified by age, the extent of coronary disease (BCIS-1 JS <12 vs. 12), degree of LV dysfunction (EF <20% vs. ≥20%), diabetes, NYHA class (<3 vs. ≥3) and chronic total occlusion (CTO). In addition, a model will be developed and patients will be categorised according to their baseline risk of the primary outcome and this will be used to examine whether the impact of treatment depends on a person's underlying risk. Since the subgroup analyses are secondary analyses and exploratory in nature, the trial has not been

powered for these. A Cox proportion hazards model incorporating tests of interaction will be used for subgroup analyses.

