4.2 Sample Size

The predicted occurrence of death or hospitalisation for heart failure at 2 years is 36% in the OMT group. The primary endpoint in REVIVED-BCIS2 will be measured over the entire trial duration, with a minimum follow-up duration of 2 years, thus increasing the number of events. A trial of 700 (350 in each group), with 300 patients experiencing primary outcome events, would have over 85% power to detect a hazard ratio of 0.7 (a 30% relative reduction in the hazard) at 5% significance allowing for up to 5% losses by the end of follow-up and increasing recruitment over time. For illustrative purposes this represents a reduction to 27% of patients with an event in the PCI group at two years.

The hazard ratio of 0.7 is considered clinically meaningful and in line with the magnitude of benefit observed across other treatment modalities in this population. For the major secondary endpoint of LVEF, even one-half of this sample size will provide 90% power to detect a minimum difference in LVEF of 4%, assuming a standard deviation of 11%.

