9 EVALUATION OF EFFICACY PARAMETERS

9.1 Analysis of Primary Outcome Variable: All-cause Death or Hospitalisation due to Heart Failure

The primary analysis will be a comparison of the incidence of all-cause death or hospitalisation due to heart failure over all available follow-up between the intervention (treatment with PCI) and control (OMT alone) arms of the trial. An REVIVED SAP

unadjusted time-to-event analysis will be performed on the primary endpoint, with the time to the first event (or censoring) measured from randomisation on an ITT basis. Hazard ratios together with associated confidence intervals will be calculated from the Cox proportional hazards model. A p-value for the treatment difference will be calculated using a likelihood ratio test. The proportionality assumption underlying the Cox model will be assessed via Nelson-Aalen plots by treatment group and by a more formal test comparing treatment hazard ratios across appropriate pre-specified follow-up time bands. If there is clear non-proportionality, comparisons will also be made in early and later follow-up using cut-points at 6 months, 1 year, and 2 years. Cumulative event rates will be calculated and presented using Kaplan-Meier time-to-event curves. As a measure of absolute treatment difference, cumulative event rates based on Kaplan-Meier estimates will be compared at 2 years and a 95% confidence interval for the difference calculated. Losses to follow-up are expected to be minimal and patients will be included up until the time they experience the event or are censored.

A secondary sensitivity analysis will be performed for the primary endpoint using a Cox model adjusted for those risk factors identified in the risk score model developed for subgroup analysis (Section 6.5.5).

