9.4 Repeat Hospitalisation due to Heart Failure and Death

To take account of recurrent hospitalisations due to heart failure, while also accounting for the competing mortality, a parametric joint frailty model will be used. The aim is to analyse repeat hospitalisations due to heart failure while accounting for their associated mortality risk. This will be achieved by specifying distributions for recurrent hospitalisations due to heart failure as well as for time to death and including individual-specific latent variables to allow for an association between the two event processes. This would yield a hazard ratio and 95% CI for recurrent hospitalisations due to heart failure (which accounts for mortality as informative censoring) as well as a hazard ratio and 95% CI for all-cause mortality. We will also undertake a negative binomial model to mitigate any potential issues in the development with the above model.⁷⁻⁹

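### Kaplan-Meier cumulative rates are prescribed for secondary events that compete with death: they overstate absolute risk by about 1-2 points at 2 years for first heart failure hospitalisation, and by more on later curves

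*Protocol*

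**What the plan says.** SAP Section 9.3 lists six time-to-event secondary outcomes: (1) cardiovascular death, (2) all-cause death, (3) HF hospitalisation, (4) acute MI, (5) appropriate ICD therapy and (6) unplanned revascularisation. It then states: "The above secondary time to event outcomes (1-6) will be analysed using the same methods as described for the primary outcome (Section 9.1").

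Section 9.1 prescribes a Cox model and adds that "Cumulative event rates will be calculated and presented using Kaplan-Meier time-to-event curves". For the absolute treatment effect, "cumulative event rates based on Kaplan-Meier estimates will be compared at 2 years and a 95% confidence interval for the difference calculated". A patient has two possible statuses: "patients will be included up until the time they experience the event or are censored". Death before the event of interest has no status of its own.

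Protocol Section 8.3 has the same rule: "other secondary time to event outcomes will be analysed using the above methods". SAP Section 9.6.2 applies the Section 9.1 methods to time to ICD or CRT implantation.

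For event outcomes, competing mortality is modelled in one place, SAP Section 9.4: "To take account of recurrent hospitalisations due to heart failure, while also accounting for the competing mortality, a parametric joint frailty model will be used". Its stated outputs are hazard ratios for recurrent hospitalisation and for death. No section specifies a cumulative incidence function for outcomes 1 or 3-6, or for device implantation.

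**The concern.** Section 9.1 suits the endpoint it was written for. The primary composite includes all-cause death, so no death competes with it. The same is true of all-cause death itself.

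The other outcomes differ. A patient who dies before a first HF hospitalisation, MI, revascularisation, ICD therapy or device implantation can no longer have that event. A patient who dies of a non-cardiovascular cause cannot die of a cardiovascular one. Under Section 9.1 these patients are censored and so treated as still able to have the event. One minus Kaplan-Meier then estimates risk in a hypothetical population without the competing deaths, and it exceeds the proportion of patients who actually have the event.

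At stake are the reported absolute risks, the component curves and the 2-year risk differences for these endpoints. The trial has high mortality and, by SAP Section 11.2, up to 8 years of follow-up. If PCI changes mortality, the two arms are distorted by different amounts.

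**Working it through.** **The plan's own figures first.** SAP Section 4.2 says: "The predicted occurrence of death or hospitalisation for heart failure at 2 years is 36% in the OMT group". It also says that the trial, "with 300 patients experiencing primary outcome events, would have over 85% power to detect a hazard ratio of 0.7". With 300 events, hazard ratio (HR) 0.7, two-sided 5% (sidedness is assumed) and 1:1 allocation, Schoenfeld's formula gives 87.1% power and Freedman's 86.4%. The stated figure reproduces. The illustrative PCI rate also reproduces: 1 − 0.64^0.7 = 26.8%, against the stated 27%.

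**Model.** Take constant cause-specific hazards: h for first HF hospitalisation and d for death before it.
- One minus Kaplan-Meier with deaths censored estimates 1 − exp(−h·t).
- The proportion who have the event is the cumulative incidence (CIF), h/(h+d) × [1 − exp(−(h+d)·t)].
- The plan's 36% at 2 years fixes h + d = −ln(0.64)/2 = 0.2231 per year.

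**Choices of d.** The documents give no rate of death before a first HF hospitalisation, so a range is used. Three values come from mortality figures in protocol Sections 2.3 and 2.4, applied in full:
- 33% at 51 months in the earlier PCI cohort: −ln(0.67)/4.25 = 0.094
- 41% over an average of 4.7 years in the medical arm of the surgical trial: −ln(0.59)/4.7 = 0.112
- 46% at 56 months, given elsewhere for that same arm: −ln(0.54)/4.667 = 0.132

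Two lower values, 0.03 and 0.055, are assumptions. They allow for deaths that follow a first hospitalisation and so do not compete with it.

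**First HF hospitalisation, OMT arm (%, Kaplan-Meier / CIF)**

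| d per year | h per year | 2 years | 5 years | 8 years |
|---|---|---|---|---|
| 0.030 | 0.193 | 32.0 / 31.2 | 61.9 / 58.2 | 78.7 / 72.0 |
| 0.055 | 0.168 | 28.6 / 27.1 | 56.9 / 50.7 | 73.9 / 62.7 |
| 0.094 | 0.129 | 22.7 / 20.8 | 47.5 / 38.8 | 64.3 / 48.1 |
| 0.112 | 0.111 | 19.9 / 17.9 | 42.6 / 33.4 | 58.8 / 41.4 |
| 0.132 | 0.091 | 16.7 / 14.7 | 36.6 / 27.4 | 51.8 / 34.0 |

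At 2 years the excess is 0.9 to 2.0 points. In the three rows with full mortality it is about 9 points at 5 years and 16-18 points at 8 years. In the two rows with lower assumed hazards it is about 4-6 points at 5 years and 7-11 points at 8 years.

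**2-year risk difference, OMT minus PCI (points, Kaplan-Meier / CIF)**

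| d per year | HR 0.7 on both hazards | HR 0.7 on death only |
|---|---|---|
| 0.094 | 6.2 / 5.3 | 0.0 / −0.6 |
| 0.112 | 5.5 / 4.6 | 0.0 / −0.6 |
| 0.132 | 4.7 / 3.7 | 0.0 / −0.6 |

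In the first scenario Kaplan-Meier makes the difference too large. In the second it shows none, although slightly more PCI patients are hospitalised because more survive to be at risk.

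**Other endpoints.** The documents give no rates for these, so the following are illustrations.
- *Cardiovascular death*, with 10-30% of deaths assumed non-cardiovascular: overstated by 0.1-0.6 points at 2 years and 0.8-3.2 points at 5 years.
- *An event with an assumed 10% net 2-year risk* (such as MI or revascularisation), with full mortality: 10.0% against 8.8-9.1% at 2 years, and 23.2% against 17.2-18.7% at 5 years.

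**The case against.** The strongest reply is that the error is small where the plan makes its formal absolute comparison, at 2 years. With 350 patients per arm and a risk near 19%, the 95% half-width of a risk difference is 1.96 × √(2 × 0.19 × 0.81/350) = 5.8 points, so a bias of 1 point or less lies well within sampling error. This stands. The large gaps affect the later part of the curves.

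A second reply is that all-cause mortality overstates the hazard of death before a first hospitalisation. This also stands, and it is why the lower assumed values are shown. They reduce the 2-year excess to 0.9-1.4 points but do not remove it.

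A third reply points to mitigation. Section 9.4 models recurrent hospitalisation jointly with death, Section 9.5 ranks death above hospitalisation, and all-cause death is reported separately. These help interpretation, but none yields a cumulative incidence for the affected endpoints.

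A reader might infer three stronger things that the documents do not support:
- *That all reported risk differences are wrong and too high.* The direction is not fixed, as the death-only scenario shows, and at 2 years the error is small.
- *That long follow-up makes the error large for every endpoint listed.* ICD therapy and device implantation data stop at 2 years. For cardiovascular death, protocol Section 4.4 leaves only deaths with evidence of a non-cardiovascular cause to compete.
- *That the hazard ratios are invalid.* A Cox model that censors at competing deaths gives a valid cause-specific hazard ratio.

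**Conclusion.** The point holds for absolute measures. SAP Sections 9.3 and 9.6.2 and protocol Section 8.3 carry a Kaplan-Meier method, correct for the primary composite, over to endpoints where it overstates the proportion of patients affected.

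For first HF hospitalisation the overstatement is about 1-2 points at 2 years, for competing death hazards of 0.03-0.13 per year. The 2-year difference is off by about 1 point or less, in either direction. If full mortality applies before a first hospitalisation, the curves run about 9 points high at 5 years and 16-18 points at 8 years. MI and revascularisation curves, which run to the last annual visit, are affected in the same way. The error is small for cardiovascular death, ICD therapy and device implantation.

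These sizes rest on constant hazards, the planned 36% OMT rate and the assumed values of d. The primary result, all-cause death and the Cox hazard ratios do not change. The correction should be made because the bias is known and avoidable, but it does not threaten the trial's main conclusion.

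**What to change.** In SAP Section 9.3 (outcomes 1 and 3-6) and Section 9.6.2, replace the Kaplan-Meier cumulative rates with Aalen-Johansen cumulative incidence. The competing event is death, or non-cardiovascular death when the outcome is cardiovascular death. Take the 2-year difference and its 95% confidence interval from these estimates. Keep the Cox model and label its result a cause-specific hazard ratio. Keep Kaplan-Meier for the primary composite and for all-cause death. Align protocol Section 8.3 with this wording.

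The cost is about one sentence in the SAP and a standard software routine. No new data are needed, because all-cause and cardiovascular death are already trial endpoints.
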